Population	
Key Inclusion Criteria
 
 • Age ≥ 18 years • Type 1 or type 2 diabetes • At least one eye with each of the following: 
 • Best corrected E-ETDRS visual acuity letter score ≥ 79 (i.e., 20/25 or better) • Ophthalmoscopic evidence of central-involved DME in study eye confirmed by CST on spectral domain OCT: 
 ▪ Zeiss Cirrus: ≥ 290 μm in women, and ≥ 305 μm in men ▪ Heidelberg Spectralis: $\geq 305\mu\text{m}$ in women, and ≥ 320 μm in men 
Key Exclusion Criteria
 
 • No history of prior laser, surgical, intravitreous, or peribulbar treatment for DME or DR in the study eye within the prior 12 months 
 ○ If more than 12 months ago, no more than 4 prior intraocular injections ○ Enrollment will be limited to a maximum of 15% of the planned sample size with any history of anti-VEGF treatment and a maximum of 15% with any history of PRP.

SUBJECT AREA	DESCRIPTION
Sample Size	134
Treatment Groups	Random assignment (1:1) to photobiomodulation (PBM) or sham
Participant Duration	The trial will last up to 12 months for each participant (primary outcome at 4 to 8 months and final visit at 8 to 12 months)

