833 A test of superiority will be used in evaluating the following hypotheses for the primary outcome:

834 Null Hypothesis (H_0): There is no difference in the mean change in CST from baseline to 4 months
835 between photobiomodulation (PBM) and sham groups.

836 Alternative Hypothesis (H_a): There is a difference in the mean change in CST from baseline to 4
837 months between PBM and sham groups.

838 Similar hypothesis tests will be conducted for all secondary, exploratory, and safety outcomes.

839 **7.3 Sample Size**

840 **7.3.1 Outcome Projections:**

841 To estimate the standard deviation (SD) of change in OCT CST, data from the DRCR Retina
842 Network Protocol A (Treatment for Central-Involved Diabetic Macular Edema in Eyes with Very
843 Good Visual Acuity) was used. The Protocol A cohort of eyes with 20/25 baseline visual acuity
844 and central subfield thickening treated with modified-ETDRS laser was used for the estimation.
845 In protocol A, 42 eyes in the modified-ETDRS laser group completed a visit within 4 months of
846 randomization. The SD of change in CST adjusted for baseline CST in these eyes was 50 microns
847 (personal communication, [name]). The mean change in CST was -2 microns.

848 The expected change and standard deviation of CST in an untreated group is unknown at this time.

849 **7.3.2 Sample Size Estimates**

850 Table 1 shows total sample size estimates under several scenarios. These calculations assume a
851 Type I error rate of 5%, 90% power, and a two-sided test of superiority (see Section 7.6) with a
852 null hypothesis of no difference between the groups (see Section 7.2).

853

854 **Table 1: Total Sample Size Under Various Assumptions for True Mean Change and**
 855 **Standard Deviation**

Mean Treatment Group Difference, microns	Change in Central Subfield Standard Deviation, microns (adjusted for baseline)			
	40	50	60	70
20	172	266	382	518
30	78	120	172	232
40	46	68	98	132

856 Assuming an effective standard deviation of 50 microns and a true difference in mean CST of 30
 857 microns, the required total sample size is 120 eyes to achieve 90% power. Sample size will be
 858 increased to 134 eyes to account for 10% lost to follow-up.

859 **7.4 Outcome Measures Phase 1 (Baseline to completion of the 4-Month/Primary outcome**
 860 **visit)**

861 *Primary Efficacy Endpoint(s)*: Mean change in CST from baseline

862 *Secondary Efficacy Endpoint(s)*:

- 863 • Mean change in retinal volume from baseline

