978 ○ Mean change in CST between 4-month and the final visit
979 ○ Mean change in retinal volume between 4-month and the final visit
980 ○ Percentage of eyes with CST below OCT machine and gender-specific threshold
981 for DME at final visit
982 • Effect on DME in eyes previously receiving sham that switch to active
983 ○ Mean change in CST between 4-month and the final visit
984 ○ Mean change in retinal volume between 4-month and the final visit Percentage of
985 eyes with CST below OCT machine and gender-specific threshold for DME at the
986 final visit
987 • Patient compliance

988 For continuous outcomes, median and interquartile ranges and/or means and standard deviations
989 will be reported to describe the data. Only participants with available CST at the primary outcome
990 visit that did not already receive alternative DME treatment will be included. No statistical
991 comparisons will be performed in Phase 2 to compare treatment groups.

992 **7.11 OCT Angiography Ancillary Study**

993 At a subset of sites with OCT angiography capabilities, images will be taken at baseline and 4
994 months to explore whether there are changes in any features evident on OCT angiography.

995 **7.12 Intervention Adherence**

996 For the primary analyses at the end of Phase 1, adherence will be defined as compliance with
997 device use during the primary outcome phase. An exploratory dose response analysis will be

998 performed to evaluate whether there appears to be an association of compliance (defined as the
999 total number of sessions of the study device use during the primary outcome phase) versus
1000 magnitude of treatment effect (defined as the change in OCT CST from baseline at primary
1001 outcome visit). The distribution of the total number of sessions will be described using summary
1002 statistics and graphical methods. A scatter plot with a regression line will be constructed to
1003 examine for evidence of dose-response, separately for each treatment group. If there is evidence
1004 of a dose-response effect in either or both groups, an analysis of covariance will be performed
1005 including treatment, compliance, and the interaction between treatment group and compliance to
1006 test for evidence that the dose-response effect is limited to the active treatment group. If the
1007 interaction between compliance and treatment group is significant, a stratified analysis will be

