279 prescribed sessions of the study device use completed during Phase 1) versus magnitude of

280 treatment effect (defined as the change in OCT CST from baseline at the primary outcome visit).

281 The analysis will include all randomized eyes. Eyes that are lost to follow-up or receive an

282 alternative DME treatment will be considered missing for change in OCT CST and compliance,

283 from the time of dropout or initiation of alternative DME treatment. Markov chain Monte Carlo

284 (MCMC) multiple imputation will be used to handle missing data for change in CST and

285 compliance. For eyes receiving alternative DME treatment, after the multiple imputation is

286 performed, the imputed change in CST will be replaced with the last observed CST prior to

287 receiving treatment (i.e. LOCF will be used). The imputation model will be stratified by

288 treatment group and will include the CST measured at baseline and at all monthly interim visits

289 through Phase 1, cumulative compliance (as defined above) through Phase 1, number of days

290 from randomization to the last completed visit (through Phase 1), along with the randomization

291 stratification factor of recent or planned intravitreous treatment in the non-study eye. For eyes

292 that complete the primary outcome visit, the actual visit date will be used for calculating the

293 number of days since randomization, regardless of alternative DME treatment; for eyes that are

294 lost to follow-up, the target visit date will be used. The distribution of the total number of

295 sessions through the primary outcome visit will be described using summary statistics and

296 graphical methods. A scatter plot with a regression line will be constructed to examine for

297 evidence of dose-response, separately for each treatment group.

298 As a dose-response effect is expected only in the active treatment group, and the study is not

299 powered to detect a significant interaction between treatment and compliance, a stratified

300 analysis will be performed using the imputed dataset at the primary outcome visit to evaluate the

301 potential association between compliance and treatment effect separately within each treatment
302 group. The stratified analysis will include adjustment for baseline CST, randomization
303 stratification factor, and number of days from randomization to the primary outcome visit. Model

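### SAP 4.0 replaces the protocol's conditional treatment-by-compliance interaction with separate within-arm analyses, which do not compare the dose-response slopes of PBM and sham

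*SAP*

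**What the plan says.** Protocol 7.12 describes an exploratory dose-response analysis of compliance against change in CST. It starts with a scatter plot and regression line for each arm. The next step is conditional: given evidence "of a dose-response effect in either or both groups, an analysis of covariance will be performed". That model is described as "including treatment, compliance, and the interaction between treatment group and compliance to" test whether the association is confined to the active arm. A within-arm analysis follows only if the interaction is significant. The same section accepts that the study is not powered for this question, and keeps the test.

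SAP 4.0 keeps the plots but removes the interaction step. It gives two reasons: dose-response is expected only under active treatment, and the study is not "powered to detect a significant interaction between treatment and compliance, a stratified" analysis is therefore run in each arm. This within-arm model adjusts for baseline CST, the stratification factor and days from randomization to the primary outcome visit, and uses the imputed dataset. SAP 4.0 plans no treatment-by-compliance term or slope difference anywhere. The later ANCOVA on four compliance categories does not list treatment among its terms.

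The SAP keeps other interactions that it says are low-powered: treatment by text reminder in SAP 4.0, and treatment by subgroup in SAP 2.1.4.

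**The concern.** The protocol asks whether a compliance gradient is specific to PBM. The SAP turns that question into a premise and plans two analyses that cannot answer it. A significant slope in one arm and a non-significant slope in the other do not show that the slopes differ.

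This matters because compliance is not randomized. Both documents say that it may depend on post-randomization factors, including masking and perceived effect, and that the observed associations may be biased. If participants who use the device more tend to have better CST change whichever device they hold, both arms will show a slope. By chance, only the PBM slope may then reach significance.

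The SAP warns about low power and about bias. It does not warn that the two within-arm results make no comparison between arms. The pilot is meant to inform whether a pivotal trial has merit, after evaluation of all the data, and a gradient wrongly taken to be PBM-specific could colour that judgement.

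**Working it through.** **Design figure.** Protocol 7.3.2 uses a "Type I error rate of 5%, 90% power, and a two-sided test of superiority". It continues: "Assuming an effective standard deviation of 50 microns and a true difference in mean CST of 30" "microns, the required total sample size is 120 eyes to achieve 90% power". Allocation is stated as "Random assignment (1:1) to photobiomodulation (PBM) or sham". The t-based calculation gives 60 per arm (power 0.903), 120 in total; the normal approximation gives 59 per arm. Sample size is then "increased to 134 eyes to account for 10% lost to follow-up": 120/0.9 = 133.3, rounded up to 134, or 67 per arm. The plan's figures reproduce. Neither document gives a sample size or power for the dose-response analysis.

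**Assumption.** The documents give no slope and no correlation between compliance and CST change. I take a within-arm correlation r from 0.1 to 0.4. With the protocol's SD of 50 microns, r corresponds to 50 × r microns per SD of compliance: 5, 10, 12, 15 and 20 microns at r = 0.1, 0.2, 0.24, 0.3 and 0.4.

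**Within-arm tests with identical true slopes.** For n eyes per arm, the noncentrality of the slope test is r/√(1−r²) × √n, on n−2 degrees of freedom. Let P be its power at two-sided 0.05. The arms are independent, so the chance of *PBM significant, sham not* is P(1−P), which cannot exceed 0.25. Example at r = 0.2, n = 60: noncentrality 0.204 × 7.746 = 1.58, P = 0.343, and 0.343 × 0.657 = 0.225.

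| r | P, n=60 | P(1−P) | P, n=67 | P(1−P) |
|---|---|---|---|---|
| 0.1 | 0.119 | 0.105 | 0.128 | 0.112 |
| 0.2 | 0.343 | 0.225 | 0.377 | 0.235 |
| 0.24 | 0.469 | 0.249 | 0.513 | 0.250 |
| 0.3 | 0.668 | 0.222 | 0.718 | 0.203 |
| 0.4 | 0.914 | 0.079 | 0.941 | 0.056 |

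A simulation of 20,000 trials per scenario, with compliance drawn at random, agrees closely. For r from 0.2 to 0.3 it gives 21-25%. At r = 0.4 it gives 9.3% (n = 60) and 6.4% (n = 67).

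**Slope-difference test with identical true slopes.** The simulated rejection rate is 4.8% to 5.4%. Among simulated trials that show the split pattern at r = 0.2 to 0.3, only about 10-11% also have a significant interaction.

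**Slope-difference test when only PBM has a slope.** The noncentrality is divided by √2, on 2n−4 degrees of freedom. Power for n = 60 to 67 is about 20-22% at r = 0.2, 40-44% at r = 0.3 and 66-71% at r = 0.4. The simulation is somewhat lower (38-41% at 0.3, 60-65% at 0.4). It holds total SD equal across arms, which leaves more residual variation in sham.

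All of these calculations ignore covariates and imputation.

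**The case against.** The strongest reply is that the SAP never states the faulty inference. Its stated aim is to see whether an association is apparent, arm by arm, and it has no rule that the split pattern establishes PBM specificity. That stands. A reader might infer that the SAP will claim specificity from two separate tests, but its text supports only the possibility of such a reading, helped by its stated expectation about the active arm.

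The change is also deliberate and explained, and Protocol 7.1 calls its own chapter a framework for the final plan. So this is not an unexplained contradiction. Nor does the protocol always fit the interaction; it does so only after evidence of dose-response. In one respect the SAP goes further, because it always examines the sham slope. A reader could difference the two reported slopes, although the SAP does not plan it.

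Low power is a fair description but a weak reason to omit the contrast. The protocol accepted it, and the SAP accepts it for other interactions.

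The last objection limits the remedy. One might infer that the sham slope controls for adherence-related confounding, so that the difference in slopes is unbiased. The documents do not support that. Masking and perceived effect can differ by arm, and so can the bias they cause. The 5% error rate holds only if the slopes, including any part due to confounding, are equal.

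**Conclusion.** The point holds as a minor one. SAP 4.0 removes the only planned contrast that addresses the protocol's own question, and the within-arm analyses do not replace it.

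With equal true slopes and 60 to 67 eyes per arm, the misleading split arises in about 10-11% of trials at r = 0.1, 23% at r = 0.2, at most 25% near r = 0.24, 20-22% at r = 0.3 and 6-8% at r = 0.4. A slope-difference test would reject in about 5%. The size therefore depends on an assumed correlation, and the 25% is a ceiling rather than a typical value.

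A reader might infer that the trial's main result is at risk. It is not: the analysis is labelled exploratory, and SAP 8.6 rests the primary conclusion on the pre-specified primary analysis.

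**What to change.** In SAP 4.0, keep the within-arm slopes and label them descriptive. Add one exploratory ANCOVA with treatment, compliance and their interaction, using the same covariates and imputed data as the within-arm analysis. Report the difference in slopes with its 95% CI. State that a significant slope in PBM beside a non-significant one in sham will not be read as PBM-specific dose-response. Extend the existing bias caveat to the slope difference, since the determinants of compliance may differ by arm.

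The cost is one model that the protocol already describes. It needs no new data. It should need no new imputation either, because the SAP's imputation for this analysis is already stratified by arm and includes both CST and compliance. The downside is a wide interval and low power for modest slopes, so the result should be presented as an estimate and not as a verdict on specificity. This is a cheap improvement.

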304 assumptions will be checked, and transformation or categorization of compliance will be used if
305 there is evidence of non-linearity in the dose response. It is recognized that the study may not be
306 adequately powered to detect a definitive dose-response association existing only in the active
307 treatment group, and lack of significance is not necessarily an indication that the association does
308 not exist. It is also recognized that compliance may be affected by both measured and
309 unmeasured post-randomization factors, including efficacy of masking and perceived effects of
310 the treatment; hence, the observed dose-response associations may be biased.

311 If compliance lessens over time during Phase 1, an exploratory analysis will investigate whether
312 there appears to be any association of compliance versus magnitude of treatment effect over
313 those months. A 4-category variable for compliance will be created from the imputed dataset,
314 based on the compliance in the first 2 months and the remainder of Phase 1, using a cutoff at
315 80% compliance for each period. Thus the overall primary outcome compliance will be
316 categorized into: 1) $\geq 80\%$ compliance in both periods, 2) $\geq 80\%$ compliance in the first 2-month
317 period but not the second period, 3) $\geq 80\%$ compliance in the second period but not the first
318 period, and 4) $< 80\%$ compliance in both periods. A box-plot for change in CST at the primary
319 outcome visit by compliance category will be created, and global test will be performed to test
320 the association between compliance and change in CST using ANCOVA adjusting for baseline
321 CST level, number of days from randomization to the primary outcome visit, and randomization
322 stratification factor. Any compliance category with fewer than 20 eyes will be excluded from the
323 ANCOVA analysis. If a significant association is found by the global test, the contrast between
324 categories 1) and 2) will be tested.

325 For Phase 2, adherence will be evaluated in a similar fashion to assess whether compliance
326 affects the post-switch effect within the initial sham group, specifically:

327 • For the initial sham group, whether there is an association between compliance during
328 phase 2 and treatment effect in phase 2, which is defined as the change in CST from the
329 primary outcome to 4 months post outcome visit.

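### The exploratory four-category compliance ANCOVA lists no treatment term, so a PBM effect combined with unequal compliance between arms can pass as a compliance effect

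*SAP*

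**What the plan says.** SAP 4.0 (Intervention Adherence) plans an exploratory analysis to be run only if compliance falls off during Phase 1. Compliance in the first two months and in the rest of Phase 1 is cut at 80%, giving four categories: high in both periods (1), high then low (2), low then high (3), low in both (4). A global test then examines "the association between compliance and change in CST using ANCOVA adjusting for baseline" followed by "CST level, number of days from randomization to the primary outcome visit, and randomization" stratification factor. Categories with fewer than 20 eyes are dropped. If the global test is significant, category 1 is contrasted with category 2.

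The categories come from the imputed dataset, which SAP 4.0 builds from all randomized eyes. Treatment group is not among the covariates, and neither the model nor the box-plot is described as being by arm.

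The rest of the section deals with arm explicitly. The scatter plots and the continuous dose-response regression are done separately in each treatment group, with the reason that begins "As a dose-response effect is expected only in the active treatment group, and the study is not" powered for a treatment-by-compliance interaction. The text-message ANCOVA includes treatment and its interaction with the reminders, because control participants may be less compliant. Protocol 7.12 also put treatment, compliance and their interaction into its dose-response ANCOVA.

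**The concern.** In a pooled model without a treatment term, compliance category stands in for arm whenever the two arms fill the categories in different proportions. If PBM lowers CST and PBM users more often stay compliant, category 1 holds more PBM eyes than category 2 and shows a larger CST reduction even if the number of sessions makes no difference. If sham users comply better, the artefact reverses sign and can hide a real dose-response.

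There is a second cost when compliance is equal. Any association confined to PBM, which is where the SAP expects it, is averaged with sham eyes that carry none.

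At stake is how the compliance results are read: sustained use could be reported as driving the anatomic benefit when the data show only that PBM differs from sham.

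**Working it through.** **Inputs from the documents.** Protocol 7.3.2 specifies a "Type I error rate of 5%, 90% power, and a two-sided test of superiority". It continues "Assuming an effective standard deviation of 50 microns and a true difference in mean CST of 30" microns, for which "the required total sample size is 120 eyes to achieve 90% power", then "increased to 134 eyes to account for 10% lost to follow-up". The Protocol Summary gives "Random assignment (1:1) to photobiomodulation (PBM) or sham", so 134/2 = 67 eyes per arm. SAP 4.0 supplies the 20-eye minimum and the covariate list.

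**Reproducing the plan's own figure.** The normal formula gives n per arm = 2(1.960 + 1.282)² × 50² / 30² = 58.4, so 59 per arm and 118 in total. The t-based version gives 59.35, so 60 per arm and 120, as stated. Allowing for loss, 120/0.90 = 133.3, so 134, as stated. The documents give no figure for the four-category ANCOVA itself.

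**Expected bias.** With PBM effect Δ and no compliance effect within either arm, the expected difference is

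category 1 minus category 2 = Δ × (PBM share of category 1 − PBM share of category 2).

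Example: if 55% of PBM eyes and 35% of sham eyes are in category 1, and 20% and 30% in category 2, the PBM shares are 0.55/0.90 = 0.611 and 0.20/0.50 = 0.400. The spurious difference is −30 × 0.211 = −6.3 microns.

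**Simulation.** 134 eyes, 67 per arm, residual SD 50, Δ = −30 microns, no compliance effect, categories under 20 eyes dropped, global F test at 0.05, 5,000 trials per scenario. Baseline CST, days and stratum were left out because they are unrelated to arm and category in this set-up. Imputation was not modelled. **The category splits are assumptions; the documents give none.**

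| Categories 1/2/3/4, PBM (%) | Same, sham (%) | PBM share, cat. 1 and cat. 2 | Spurious 1 − 2 difference (microns) | Rejection, no treatment term | Rejection, treatment added |
|---|---|---|---|---|---|
| 45/25/10/20 | 45/25/10/20 | 0.500, 0.500 | 0 | 4.6% | 5.0% |
| 50/22/10/18 | 40/28/10/22 | 0.556, 0.440 | −3.5 | 5.5% | 4.8% |
| 55/20/10/15 | 35/30/10/25 | 0.611, 0.400 | −6.3 | 8.4% | 5.0% |
| 65/15/10/10 | 30/30/10/30 | 0.684, 0.333 | −10.5 | 18.1% | 5.3% |
| 35/30/10/25 | 55/20/10/15 | 0.389, 0.600 | +6.3 | 9.1% | 5.0% |

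The simulation standard error near 5% is √(0.05 × 0.95/5,000) = 0.3 points, so the second row is barely distinguishable from nominal. In the third row, a PBM effect of 20 microns gives 6.5% and one of 40 microns gives 12.5%. With no PBM effect, rejection without a treatment term stays at 4.6% to 5.6% across all five splits.

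**Another way to set the splits.** Assume period-specific compliance rates instead. With 85% versus 60% compliant in the first period and 60 eyes per arm, one set of second-period assumptions gives 12.5%. Varying the second-period rates and the between-period correlation gives 7.3% to 12.8%, or 8.4% to 15.0% at 67 per arm. With 80% versus 65%, rejection is 6.7%. With 80% versus 75% and then 60% versus 55%, it is 5.0% to 5.7%.

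**Dilution.** Assume equal compliance, 45% of eyes in each of categories 1 and 2, and a 40-micron benefit confined to PBM eyes in category 1. The pooled global test then has about 55% power, the pooled test with a treatment main effect about 56%, and the same test within PBM about 85%. A main effect removes the confounding but not the averaging.

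**Fitting within arm under the 20-eye rule.** All four categories cannot survive, since 4 × 20 = 80 exceeds 67. In the order of the table rows, two or more PBM categories reach 20 eyes in 24.6%, 9.3%, 3.8%, 0.2% and 59.6% of trials.

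**The case against.** The strongest reply is that pooling is not stated. The preceding dose-response regression is fitted within each arm with the same three covariates, and a within-arm model has no treatment term, so the four-category analysis could be a continuation of it. The 20-eye rule does not settle this, because it drops small categories without requiring all four to survive. This stands as a limit: pooling is inferred. It remains the natural reading, given a dataset of all randomized eyes and a section that names arm wherever it wants arm handled. If by-arm fitting was meant, the SAP needs to say so, and the 20-eye rule would then often leave nothing to test.

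Second, the analysis is exploratory and conditional, and the SAP warns that dose-response associations may be biased by post-randomization factors. The arm-specific regressions also offer a check. This limits the seriousness. The warning does not name confounding by arm, however, and that source can be removed because treatment is known for every eye.

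Third, participants are masked, and the SAP calls lower sham compliance only possible. Compliance may turn out similar, in which case the false-positive rate is about nominal. This also stands.

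A reader might further infer that a false result here would misdirect the pivotal trial. The documents do not support that. The compliance measures that Protocol 7.19 and SAP 6.0 name, as examples, for pivotal design are the proportion of enrolled participants who are randomized and the proportion who comply with the device. Those are rates that this ANCOVA does not change, and no design decision is tied to its result.

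**Conclusion.** The point holds as a defect in one exploratory model. Followed as listed and pooled, the ANCOVA confounds compliance category with arm if two conditions both hold: PBM affects CST, and compliance differs by arm. Under the assumed splits the inflation runs from negligible to roughly three and a half times nominal (18.1/5 = 3.6). Some versions of a large first-period imbalance give as little as 7%. The largest spurious category difference, 10.5 microns, is about a third of the 30-micron design effect.

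These figures rest on the design effect and SD and on compliance distributions that the plan does not supply. It would go too far to say that the test is sure to mislead, or that the trial's main conclusion is at risk: SAP 8.6 bases that conclusion on the primary analysis alone, which this model does not touch. The correction is worth making because it is simple and matches how the SAP treats arm in its text-message ANCOVA.

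**What to change.** Add treatment group as a covariate in the four-category ANCOVA, both for the global test and for the category 1 versus 2 contrast, and draw the box-plot by arm. In the simulations this restores about 5% rejection. The cost is one model term and a sentence in the SAP; no new data are needed.

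Because a dose-response is expected only in the active arm, also report category estimates by arm from a treatment-by-category term. Label them descriptive and low-powered, consistent with the SAP's own statement about the treatment-by-compliance interaction.

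If the model is meant to be fitted within arm, say so and restate the 20-eye minimum for a single arm, since about 67 eyes will often leave fewer than two usable categories. This route costs more: the categories may need to be merged or the minimum lowered, and that choice should be fixed before the outcome data are seen by arm.
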